## Study Overview

**STUDY TITLE:** Dopaminergic enhancement of rehabilitation therapy early after stroke

**INSTITUTIONAL REVIEW BOARD (IRB) #:** 22-000104

**DESCRIPTION:** Telerehabilitation (TR) is defined as delivery of rehabilitation services via communication technologies. This study uses an established TR system and protocol to supplement usual care, and also asks whether adding a dopaminergic drug enhances TR effects. In addition, the predictive value will be examined for two biomarkers that characterize capacity for brain plasticity.

Patients with arm weakness due to a new stroke in the past 30 days will be randomized to receive [1] 6 weeks of TR + Sinemet 25/100 once/day, on top of usual care (UC), [2] 6 weeks of TR + placebo once/day, on top of UC, or [3] UC alone. TR consists of 70 minutes/day of activity targeting upper extremity (UE) function, delivered in the home and (when appropriate) initiated in the inpatient rehabilitation facility (IRF) setting. Two previously validated predictive biomarkers are hypothesized to prospectively identify treatment responders: first, extent of stroke-related injury to the corticospinal tract (CST), obtained via MRI scan; and second, a polygene score focused on dopamine neurotransmission.

The currently planned study uses very similar software and hardware as the TR system as in a prior national study that found that this TR system was safe, associated with significant gains in arm function and in global function, and had efficacy comparable to that seen when the same dose of therapy was delivered in the clinic (i.e., delivered in the same manner as standard care). In that prior study, the FDA determined (Q140628) that the investigation was a non-significant risk device study.

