**The rationale for examining whether an intact corticospinal tract is needed to benefit from TR:**

Aim 3 hypothesizes that patients with milder CST injury are more likely to achieve gains in arm function. Neural repair after stroke benefits from patient stratification, as patients with stroke are a heterogeneous population, with differing capacities to respond to rehabilitation therapy. Although several potential predictors of response to a restorative therapy in patients with subacute or chronic stroke have been identified, analysis of data from patients receiving TR in the prior national trial found that clinical measures provided limited prediction of TR-related arm motor gains. Following bivariate screening of 43 baseline clinical measures from eight categories, a multivariable linear regression model predicted only 17.6% of the variance in TR-related arm motor gains ( $p<.004$ ). Other types of measurement beyond clinical data are needed to prospectively identify treatment responders.

Neuroimaging measures are excellent candidates for predicting benefit from rehabilitation after stroke. Indeed, such measures can be superior predictors compared to clinical measures. CST injury is the focus here because it is a common pathway for TR components: the mechanism of action for TR efficacy revolves around cortical plasticity from multiple circuits driving signals down the CST--and so greater CST injury would be expected to limit treatment-related behavioral gains. Five prior studies from the [name] lab support this hypothesis, each finding that % CST injury was a significant predictor, explaining 17-33% of variance in arm motor recovery during receipt of a restorative therapy in subacute or chronic stroke. Importantly, in each of these studies, % CST injury was a better predictor than age, baseline behavioral status, and total infarct volume. For example, the largest of these studies, focused on patients in the subacute phase post-stroke, found that  $\geq 75\%$  CST injury had 91.7% positive predictive value that a patient would fail to achieve a gain on the Action Research Arm Test that reached or exceeded the minimal clinically important difference (MCID) of 5.7 points for this scale. These data suggest that treatment non-responders are common and can be accurately identified at baseline based on severity of CST injury.

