## Visit 4 (End of Study)

The end-of-study visit will generally be conducted at Cal Rehab, but accommodations for home assessment will be made as needed; this visit occurs 1 month after Visit 3. Visit 4 may be broken into more than one session, as needed. All Visit 4 assessments are available in a single “Visit 4” packet, located in the lab’s Box folder. Details regarding administration of each assessment is found within individual CRFs.

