**Aim 2. TR+Sinemet is superior to TR+placebo:** Among patients randomized to TR, gains in arm function will be greater in those who take Sinemet (25/100) prior to daily TR, as compared to patients who take placebo prior to TR.

The above analyses will be repeated but instead comparing patients randomized to [1] TR+Sinemet vs. [2] TR+placebo.

**Aim 3. Less CST injury and higher dopamine polygene score predict better recovery of arm function:** Across all subjects, change in arm function will be highest in those with lower % CST injury and in those with higher dopamine polygene scores. These relationships will remain significant when examining only patients randomized to TR. The drug X gene score interaction term will be significant such that the slope of arm gains in relation to the polygene score will be smaller (less steep) in those receiving Sinemet.

**H3A:** Using linear regression, we will test whether lower % CST injury predicts higher change in ARAT score from Visit 1 to Visit 4, after controlling for baseline ARAT score and clinical measures (age, time from stroke to randomization, and total hours of outside rehabilitation therapy from Visit 1 to Visit 4). Primary analysis will examine all enrollees. Secondary analysis will examine this relationship separately for patients randomized to one of the two TR groups, while tertiary analysis will examine this separately across all three treatment groups.

Restricted cubic splines will be used to determine if the effect of continuous covariates such as age are linear. A linear model that includes individual clinical measures will be used rather than propensity adjustment so that the effect of % CST injury can be compared to the effects of the other covariates. This approach also allows us to test the hypothesis that % CST injury predicts ARAT gains beyond what can be learned from clinical variables alone.

**H3B:** We will test whether higher dopamine polygene score predicts higher change in ARAT score from Visit 1 to Visit 4, after controlling for the same covariates as in H3A. Analyses will follow those described in H3A.

Secondary analysis will repeat H3A and H3B using change in BBT from Visit 1 to Visit 4 as the dependent measure. Tertiary analyses will repeat these methods focusing on change in FMA-UE, CES-D, mRS, NHPT, SIS-ADL, and SIS-hand scores.

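### The H3A and H3B models adjust for outside-therapy hours that accrue up to Visit 4, so they may not estimate the baseline predictive association that Aim 3 is meant to test

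*Combined protocol and SAP*

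**What the plan says.** Statistical Analysis, Aim 3, H3A: "we will test whether lower % CST injury predicts higher change in ARAT score from Visit 1 to Visit 4", by linear regression. The covariates are baseline ARAT, age, stroke-to-randomization time "and total hours of outside rehabilitation therapy from Visit 1 to Visit 4". H3B tests the polygene score "after controlling for the same covariates as in H3A". The same section says the H3A model will show whether % CST injury "predicts ARAT gains beyond what can be learned from clinical variables alone".

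Visit 4 (End of Study): "this visit occurs 1 month after Visit 3", and Visit 3 is the end of treatment.

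The purpose is stated in two places. Study Overview, Description: "Two previously validated predictive biomarkers are hypothesized to prospectively identify treatment responders". Background, in the rationale for the corticospinal tract measure: "treatment non-responders are common and can be accurately identified at baseline based on severity of CST injury".

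No H3A or H3B model restricted to baseline covariates is specified. The unadjusted results promised earlier in Statistical Analysis belong to the propensity-weighted group comparisons of Aims 1 and 2. For Aim 3 the plan says it uses individual covariates in place of the propensity score.

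**The concern.** A model meant to pick out responders in advance should use only what is known in advance. Total outside hours are complete on the day the outcome is measured, so the specified model cannot be applied to a new patient at baseline.

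Two results are affected.

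- **Added value.** The clinical comparator includes therapy not yet delivered. What CST injury adds to that comparator is not what it adds to baseline clinical information. The Background takes its own clinical benchmark (17.6% of variance in gains) from a screen of 43 baseline measures, so the Aim 3 result would not be comparable with it.
- **The biomarker slope in H3A.** If severity of injury influences how much therapy a patient receives, the hours lie partly on the path from injury to recovery, and holding them fixed changes the slope. The Background says post-discharge therapy dose varies widely, but it does not link dose to CST injury. That link is an inference.

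**Working it through.** **The plan's own figure.** No sample size or effect size is given for Aim 3. The one computed figure is for Aim 1 (difference 5.7, SD 7.4, two-sided alpha 0.05, power 80%, combined TR to UC 3:1). UC patients needed = (1 + 1/3) x (1.960 + 0.842)^2 x (7.4/5.7)^2 = 17.64, rounded to 18. With 54 TR patients the total is 72, as stated. Power at 18 versus 54 is 80.8% (normal) or 79.7% (noncentral t). This reproduces and does not bear on the present point.

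**Timing of the covariates.**

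| Term | Known at Visit 1? |
|---|---|
| ARAT at Visit 1 | yes |
| Age | yes |
| Stroke-to-randomization time | yes |
| Outside hours, Visit 1 to Visit 4 | no, complete only at Visit 4 |
| Outcome: ARAT change, Visit 1 to Visit 4 | no, same interval as the hours |

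This applies to H3A and H3B alike and needs no assumption.

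**Effect on the H3A slope (illustration).** The documents give neither an injury-hours nor an hours-gain association, so the paths are assumed. All variables are standardised and other covariates are left out.

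- Total effect of CST injury on gain: -0.45. Its square is 0.2025, about 20% of variance, inside the 17-33% that the Background reports from prior studies.
- CST injury to hours: a = 0.4 (assumed).
- Hours to gain: b = +0.2 or -0.2 (assumed).
- Adjusted slope = total - a x b.
- b = +0.2: -0.45 - 0.08 = -0.53.
- b = -0.2: -0.45 + 0.08 = -0.37.
- Relative shift: 0.08/0.45 = 18%, in either direction.

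**Effect on the added R2, same paths.** Variance added by CST injury once hours are in the model = slope^2 x (1 - a^2).

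- Without hours: 0.2025.
- b = +0.2: 0.2809 x 0.84 = 0.236.
- b = -0.2: 0.1369 x 0.84 = 0.115.

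**Range.** Take a total R2 of 17% or 33%, b = 0.3, and either no unmeasured cause of both hours and gain or one with paths 0.4 to hours and 0.3 or -0.3 to gain. The ratio of the adjusted slope to the baseline slope is then:

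- injury-hours correlation 0: 1.00;
- between -0.2 and +0.2: 0.79 to 1.21;
- between -0.4 and +0.4: 0.57 to 1.43.

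**Precision.** The variance inflation factor 1/(1 - r^2) is 1.10 at r = 0.3 and 1.33 at r = 0.5. Hours also remove residual variance of 0.04 x (1 - r^2) when the hours effect is 0.2 in size:

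- r = 0.3: 1.099 x (0.7975 - 0.0364)/0.7975 = 1.05.
- r = 0.5: 1.333 x (0.7975 - 0.0300)/0.7975 = 1.28.

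Net inflation of the slope's variance is therefore about 5% to 28%.

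**The case against.** The best defence is that the amount of therapy received is a legitimate thing to hold fixed. Dose varies widely, and the Background's mechanism is that CST injury limits what therapy can achieve. Whether injury predicts gain at a given amount of other therapy fits that mechanism. The plan also wants to compare the CST effect with the effects of the other covariates. This stands as a reason to keep the hours-adjusted model. It does not make that model a test of baseline prediction, which is the purpose given in the Study Overview.

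Other points that stand:

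- The model already adjusts for baseline ARAT, and entry is restricted to ARAT below 32. What matters is the injury-hours association that remains after the baseline covariates, and it may be small.
- The 0.08 shift is modest against sampling error. In the one-predictor setting with n = 72, the standard error is about sqrt(0.7975/70) = 0.107, so the shift is about 0.75 standard errors.
- The study is powered for Aim 1 only.

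A reader might infer that these models cannot show baseline prediction at all. The documents do not support that. If hours are unrelated to the biomarker given the baseline covariates, the slope is unchanged, and nothing in the documents says that they are related.

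A reader might also carry the mediation argument over to H3B. The polygene score is built from five genetic polymorphisms, and the documents describe no path from it to outside hours.

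Nor can the adjusted slope simply be read as a direct effect. That needs hours and gain to share no unmeasured cause.

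**Conclusion.** The point holds in a limited form. For both hypotheses, the specified model conditions on information unavailable when the biomarker would be used. It may therefore not estimate the baseline association, and the test of added value uses a comparator that contains future information.

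For H3A there is a further possibility that the slope itself shifts. Its size and direction are unknown: -0.45 becomes -0.53 or -0.37 under the illustrative paths, and nothing changes if hours and injury are unrelated given the baseline covariates. For H3B, only the timing point clearly applies.

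The change should be made because it is cheap and aligns the analysis with the stated purpose. The primary endpoint, the sample size and the Aim 1 and Aim 2 comparisons are not touched.

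**What to change.** - Specify the primary H3A and H3B models with baseline covariates only: Visit 1 ARAT, age and stroke-to-randomization time.
- Base the claim of prediction beyond clinical variables on these models.
- Report the model that adds outside hours from Visit 1 to Visit 4 as a sensitivity or explanatory analysis, labelled as conditional on therapy received during follow-up.
- Carry the same covariate set through to the secondary and tertiary endpoints that repeat H3A and H3B.

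The cost is SAP wording only, with no new data and no change to the 72 patients. The downside is that the primary model gives up whatever residual variance the hours would have explained. Under the illustrative paths (a = 0.4, b of size 0.2) that is 0.04 x 0.84 = 0.034 of the outcome variance.

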**The rationale for examining whether dopamine genetics predicts benefit from TR and benefit from Sinemet:**

**Aim 3** hypothesizes that change in arm function will be highest in those with higher dopamine polygene scores. Dopaminergic drugs have long been studied towards the goal of improving outcome via enhanced brain plasticity after neural injury such as stroke. However, results to date have been inconsistent, with motor learning and plasticity improved by dopaminergic drugs in some studies but not in others. Genetic measures might explain part of this variance and indeed might form a basis to personalize medicine by predicting which patients will be responders. Several prior studies suggest the utility of a dopamine polygene score based on 5 common and biologically active genetic polymorphisms. One study from my lab found that this polygene score can predict (a) motor learning, (b) motor cortex plasticity, and (c) their modulation with Sinemet 25/100^114. Importantly, the predictive value of this dopamine polygene score was independently validated by Diaz Heijtz at the Karolinska Institutet in a study of intensive arm motor therapy provided to hemiparetic children with cerebral palsy. Separately, my lab also found that this polygene score predicted depression scores in healthy subjects and in subjects with major depression. MacDonald et al at University of Auckland found that the same polygene score was able to predict extent of impulse control and whether these symptoms responded favorably to a dopamine agonist drug. For these reasons, this polygene score will be tested as a predictor of treatment effect in each patient group.

**A pilot study of TR in patients with chronic stroke** was an extension of the [name] lab's longstanding experience studying game-based robotic arm motor therapy for patients with stroke. A pilot study transferred these and other games to a TR system, then tested it in 12 patients with chronic (>6 months post-onset) stroke. Each patient received 4 weeks of home-based, therapist-supervised TR targeting arm motor deficits. We found that

- Patients were highly compliant (97.9% of assigned days) and rated the system favorably;
- Therapists in the clinic were able to remotely review patient performances and revise therapy;

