An additional H3B analysis will examine the drug X gene score interaction term in those patients randomized to TR (i.e., TR+Sinemet or TR+placebo). Based on our prior findings in healthy subjects, this term is hypothesized to be significant such that the slope of ARAT change in relation to the polygene score will be smaller (less steep) in those receiving Sinemet.

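### The all-enrollee H3A and H3B models omit randomized arm and any biomarker-by-TR term, so they can show prognosis but cannot support the claim that the biomarkers identify treatment responders

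*Combined protocol and SAP*

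**What the plan says.** **The models.** In the Statistical Analysis section, H3A is a linear regression of ARAT change (Visit 1 to Visit 4) on % CST injury, "after controlling for baseline ARAT score and clinical measures (age, time from stroke to randomization, and total hours of outside rehabilitation therapy"; these hours are counted over the same interval. H3B does the same for the polygene score, "after controlling for the same covariates as in H3A". Neither list contains treatment group. On the analysis set: "Primary analysis will examine all enrollees". The next step is narrower: "Secondary analysis will examine this relationship separately for patients randomized to one of the two TR groups", with a tertiary analysis by each of the three arms.

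**The one interaction.** An additional H3B analysis tests drug by gene score among TR patients, expecting that "the slope of ARAT change in relation to the polygene score will be smaller (less steep) in those receiving Sinemet". There is no counterpart for % CST injury, and none for gene score in TR versus UC.

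**What is claimed.** Aim 3 itself reads: "Across all subjects, change in arm function will be highest in those with lower % CST injury and in those with higher dopamine polygene scores". The Study Overview goes further: "Two previously validated predictive biomarkers are hypothesized to prospectively identify treatment responders". The Background rationale for the dopamine score says "this polygene score will be tested as a predictor of treatment effect in each patient group". The Background passages on CST injury likewise present it as a marker of gains due to treatment and ask whether an intact tract is needed to benefit from TR.

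**An internal comparator.** The exploratory aphasia and neglect models under Aim 1 (LAST and SCT scores) do include treatment group as a predictor.

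**The concern.** A biomarker that identifies responders to TR must have a different slope under TR than under usual care. A slope pooled over arms, or fitted in TR patients alone, cannot separate benefit from TR from recovery that would have happened anyway. This matters here because patients are randomized within 30 days of stroke, and the protocol's account of its early-stroke pilot attributes much of the gain to spontaneous recovery. The trial has a randomized UC arm that could separate the two, but the Aim 3 plan never uses it for that comparison.

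At stake is the wording of the conclusion: a marker that predicts recovery equally in every arm could be reported as predicting response to TR. Two smaller matters follow from the same models. Leaving out arm puts any treatment effect into the residual. Pooling Sinemet patients in H3B averages over slopes that the plan itself expects to differ.

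**Working it through.** **Inputs.** From Sample Size: 27 TR+Sinemet, 27 TR+placebo, 18 UC (54 TR v 18 UC); difference 5.7 points; SD 7.4; two-sided alpha 0.05; dropout up to 20%. From the Background on CST injury: 17-33% of variance explained. The documents give no effect size for the gene score and no ratio of Sinemet to placebo slopes.

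**1. The plan's own figure.** UC patients needed = (1.96+0.84)² × 7.4² × (1+1/3) / 5.7² = 17.6, so 18 and a total of 72. Power is 80.8% (normal) or 79.7% (noncentral t). The stated 72 and 80% reproduce. No power is stated for Aim 3.

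**2. A purely prognostic marker.** Suppose the slope is the same in all arms, with R² = 0.17.
- Fisher z with four covariates, n=72: atanh(√0.17) × √(72-3-4) = 0.438 × 8.06 = 3.53. Power = Φ(3.53-1.96) = 94%.
- The same at n=58 (72 × 0.8): 0.438 × √51 = 3.13. Power = Φ(1.17) = 88%.
- Simulation, 10,000 trials of 72 with a 5.7-point TR effect:

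| Model | R² 0.17 | R² 0.33 |
|---|---|---|
| All enrollees, no arm term (as planned) | 91% | 99.8% |
| All enrollees, arm added | 94% | 99.9% |
| TR patients only | 86% | 99% |
| Biomarker x TR term | 5% | 5% |

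The planned tests are usually significant for a marker that carries no information on response to TR. The interaction is significant only at the nominal rate.

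**3. Cost of omitting arm.** Added residual variance = 0.75 × 0.25 × 5.7² = 6.09, against 7.4² = 54.76 (11%). SE inflation = √(1 + 6.09/[54.76(1-R²)]) = 1.054, 1.065 and 1.080 at R² = 0, 0.17 and 0.33. At half the effect (2.85 points) the added variance is 1.52 and the inflation is 1.014 to 1.021. Under randomization, arm is unrelated to the biomarker in expectation, so this is a loss of precision and not a bias.

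**4. Pooled gene slope.** Assume the UC slope equals the placebo slope and the Sinemet slope is a fraction t of it. Pooled slope = 45/72 + (27/72)t = 0.625 + 0.375t. This gives 0.91 at t = 0.75, 0.81 at t = 0.5 and 0.63 at t = 0, as a share of the non-drug slope.

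**5. What the interaction can deliver.** SE of a TR-UC slope difference = 7.4 × √(1/54+1/18) = 2.01 ARAT points per biomarker SD, so the 95% half-width is 1.96 × 2.01 = 3.9. With placebo v UC only, SE = 7.4 × √(1/27+1/18) = 2.25 and the half-width is 4.4. At R² = 0.17 the slope itself is √0.17 × 7.4 = 3.05 points per SD. If the TR slope corresponds to R² of 0.17 to 0.33 and the UC slope is zero, interaction power is 38% to 72% (30% to 61% after 20% dropout). If the UC slope is half the TR slope, it is 13% to 25%.

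**The case against.** **The models test the hypothesis as written.** Aim 3 is about predicting recovery across all subjects, and a pooled regression is the right tool for that. This stands. The 91-94% is power for the stated prognostic hypothesis. A reader might take it as a false-positive rate for Aim 3, but it is misleading only if the result is presented as evidence of response to TR.

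**Responder may mean something weaker.** The CST rationale speaks of non-responders as patients on restorative therapy who do not reach a 5.7-point gain. The TR-only fit addresses that meaning, and the by-arm fits match the wording about each patient group. This stands in part: the usage is defensible, but the Background also speaks of benefit from TR and of treatment effect, and absolute gain this early after stroke does not show either.

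**Slopes are compared.** A reader might infer that no slopes are ever compared between arms. That is not so: the drug-by-gene term formally compares Sinemet with placebo. With 0/1 coding, the gene main effect in that TR-only model is already the placebo slope. What is missing is TR versus UC, for both biomarkers.

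**Dilution depends on the estimand.** An all-subject slope is what Aim 3 asks for. It is smaller only relative to a non-drug slope that the plan does not name as primary. This stands, and the size rests on assumptions the documents do not supply.

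**The remedy is weak.** With 18 UC patients the interaction will probably be inconclusive. This also stands, and is why it is proposed as a supportive estimate and not as a test.

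**Conclusion.** The point holds in a limited form. The primary H3A and H3B models are adequate for Aim 3 as worded, but they cannot support the statements elsewhere that the biomarkers identify treatment responders or predict benefit from TR. A marker with equal slopes in every arm at R² 0.17 would be significant in about 91-94% of trials at n=72, or about 88% at n=58. This takes 17% as the variance explained after the four covariates.

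The other effects are minor or conditional. A reader might suppose that omitting arm biases the biomarker slope. Under randomization it does not: the SE rises by about 5-8% at the full 5.7-point effect and 1-2% at half of it. The pooled gene slope would be smaller than the non-drug slope if the plan's prediction for Sinemet is right. The figures of 81% and 63% hold only if the Sinemet slope is half or zero and the UC slope equals the placebo slope. The Aim 1 primary result is not affected.

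**What to change.** 1. Add three-level randomized arm as a covariate in the all-enrollee H3A and H3B models, in line with the LAST and SCT models.
2. Report % CST injury x (TR v UC) and gene score x (TR v UC) with 95% CIs as supportive estimates, and state that they are imprecise with 18 UC patients (half-width about 4 ARAT points per biomarker SD). Make any responder or treatment-benefit claim only from these terms. Otherwise describe Aim 3 results as prognostic, and align the Study Overview and Background wording with that.
3. For H3B, fit one gene-by-arm model and report the three arm-specific slopes. For gene x TR, contrast TR+placebo with UC, because the Sinemet slope is expected to differ. Do not read the main effect as the slope off Sinemet: if gene x TR and drug x gene enter one model with 0/1 coding, the main effect is the UC slope, from 18 patients.

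**Cost.** Analysis-plan wording only, with no added patients, visits or data. The downside is that the interaction estimates will probably be inconclusive, and the plan should say so in advance.
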